In a larger report from Chinese Center for Disease Control and Prevention of 72,314 cases 14% presented with severe disease that was defined as dyspnea, respiratory frequency \geq 30, blood oxygen saturation \leq 93%, partial pressure of arterial oxygen to fraction of inspired oxygen ratio < 300, and/or lung infiltrates >50% within 24-48 hours.** Critical disease developed in 5% that resulted in respiratory failure, septic shock and/or multi-organ failure. In this report the case fatality rate (CFR) was 8.0% in patients age 70-79, 14.8% in patients over age 80, and 49% in critical cases. CFR was elevated among those with preexisting comorbid conditions: 10.5% for cardiovascular disease, 7.3% for diabetes, 6.3% for chronic respiratory disease, 6.0% for hypertension and 5.6% for cancer. A total of 1,716 infected were health care workers. Overall, 14.8% of health care workers developed severe or critical disease, and 5 deaths were observed.**

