3.1.2 Study Entry: Time from COVID-19 Infection Onset

3.1.2.1 High Risk group: Entry within 14 days of COVID-19 infection documentation.

Patients in the High-Risk group must present with either mild or non-severe disease for to be eligible for study entry; thereby, being identified early in the infection. These patients are to be entered and consented within 14 days of symptomatic COVID-19 infection documentation. Mild symptoms could include typical symptoms such as fever, dry cough, fatigue, nausea, emesis or diarrhea

3.1.2.2 Health Care Providers group: Healthcare worker must present with asymptomatic and with a positive NP swab; or mild or non-severe disease for to be eligible for study entry; thereby, being identified early in the infection. Asymptomatic patients must be enrolled within 14 days of the positive COVID-19 test. Mild or non-severe must be enrolled within 14 days of symptomatic infection documentation.

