4.1.2 Group 4: Health Care Providers with asymptomatic, mild or non-severe disease

- 1. Health care providers who as part of their activities from time to time are at risk to exposure to COVID-19 infection. This includes administrative staff and ancillary support staff associated with hospitals or ambulatory clinic facilities.
- 2. Asymptomatic is defined as having diagnosis of COVID-19 without symptoms or clinical findings.
- 3. Mild or non-severe disease: Refer above for definitions.
- 4. Informed consent signed within 14 days positive COVID-19 test.

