6.0 Statistical and Quantitative Analysis

6.1 Determination of Sample Size and Statistical Analysis

Group sequential design is employed for each hypothesis that analysis will be performed after enrolling and observing outcomes of one-third of maximum sample size. Our design includes two interim analyses and a final analysis for each hypothesis. The Pocock method is used to determine sample size and each study is sized to maintain the power of 80% and overall type I error 5%. To calculate the sample size, the large-sample Z test for a proportion is utilized for each analysis.

	Enrollment at stage 1	Enrollment at stage 2	Enrollment at stage 3	Maximum enrollment	Expected enrollment for projected proportion
Study group 3	76	76	76	228	159
Study group 4	73	73	73	219	152

Group 3

For high-risk COVID-19 infected patients that present with early mild or non-severe disease the estimated percent who will develop severe disease is 27% for those over age 65. There is insufficient data on patients who have coexisting severe immune compromised status; however, for patients that presented with diabetes or heart disease/hypertension risk was 16% - 30%, respectively. Assuming a reported risk of progression of 25%, it is postulated that the infusion of convalescent plasma will reduce the probability for progression to severe disease by a factor of 0.35 to 16.3% or lower. We will carry out 3-stage of enrollment and 76 patients are enrolled in each stage. The interim analysis will be performed after enrolling and observing outcomes of 76 patients. Our design leads to the maximum size of 219 patients after completing 3-stage of enrollment and the expected size is 159 patients.

Group 4

Among healthcare workers 14.8% of cases were classified as evolving to severe or critical per the Chinese epidemiological review. ^{24,25} It is postulated that the infusion of convalescent plasma will reduce the probability for progression from asymptomatic, mild or nonsevere disease to that of severe disease will be reduced by a factor of .5 to 7.5% or lower. We will carry out 3-stage of enrollment and 73 patients are enrolled in each stage. The interim analysis will be performed after enrolling and observing outcomes of 73 patients. Our design leads to the maximum size of 219 patients after completing 3-stage of enrollment and the expected size is 152 patients.

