6.3 Statistical Analysis

We will perform intention-to-treat analysis to analyze outcomes of all enrolled patients. The primary analysis is to evaluate the CRF or disease progression rate against the null proportion. We plan to perform two interim analyses and one final analysis. The first interim analysis will be performed after enrolling and observing outcomes of one-third of maximum sample size. At an interim analysis, CRF or disease progression rate will be reported, together with a score confidence interval for the rate. The critical value used to evaluate the confidence interval is 2.289 based on the Pocock method. We will compare the upper limit of the confidence interval with the assumed null proportion. We will conclude efficacy of the treatment if the upper limit is less than the null proportion and terminate enrollment for the relevant study group. If the upper limit is greater than the null proportion, we will proceed to the second stage of enrollment and then perform the second interim analysis on the cumulative data. The same evaluation will be replicated in the second interim analysis, as well as in the final analysis should we proceed to this step.

After completing the trial, we will conduct secondary analysis to compare outcomes of this trial with published historical experience. We will use the score test for comparing two proportions in each evaluation. We will report both p value and 95% score confidence interval for difference between two proportions.

It is acknowledged that COVID-19 viral pandemic outbreak remains dynamic. Epidemiological update reports from the CDC may result in reassessment for case fatality rates as well as case rates for disease progression used in our study design that may require adjustments in sample size determinations at the interim analysis as independently allowed by the biostatistician.

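### Group 4 tests one pooled rate for asymptomatic and symptomatic workers against 14.8%, a benchmark of unstated symptom mix, so a difference in mix can pass for an effect of plasma in either direction

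*Combined protocol and SAP*

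**What the plan says.** Group 4 takes health care providers in three entry states. Section 4.1.2 lists the asymptomatic state beside mild and non-severe disease: "Asymptomatic is defined as having diagnosis of COVID-19 without symptoms or clinical findings". Section 3.1.2.2 sets its entry window: "Asymptomatic patients must be enrolled within 14 days of the positive COVID-19 test". Neither section limits the asymptomatic share.

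The Group 4 endpoint in 3.1.1 combines the three states, and the hypothesis in 6.1 is that plasma will "reduce the probability for progression from asymptomatic, mild or nonsevere disease to that of severe disease". The benchmark comes from the same section: "Among healthcare workers 14.8% of cases were classified as evolving to severe or critical per the Chinese epidemiological review". Section 1.2 describes the denominator only as infected workers: "A total of 1,716 infected were health care workers". The target is a risk "reduced by a factor of .5 to 7.5% or lower".

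Section 6.3 analyses all enrolled patients, one rate per group. Efficacy is concluded, and enrolment of the group ends, if the upper score limit is below the null proportion at any of three looks. "The critical value used to evaluate the confidence interval is 2.289 based on the Pocock method". The only stratification named (3.1) is into treatment groups. Section 5.1.1 records days of symptoms before infusion, but no stated analysis uses them for the primary endpoint.

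**The concern.** With no control arm, 14.8% is the only comparator for the primary endpoint. It is a fair null only if the enrolled workers, untreated, would progress at 14.8%. That depends on how many of them were found by testing without symptoms, compared with the workers behind the published figure. The plan neither fixes the first share nor states the second.

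Nothing else in the plan corrects this for the primary endpoint. The matched or historical comparison in 6.2.1 is for secondary endpoints. The end-of-trial comparison with published experience in 6.3 is an unadjusted two-proportion test, so it inherits the same difference in mix. The clause on epidemiological updates concerns revised case rates and sample size, not who entered. At stake is whether a crossed boundary in Group 4 can be read as an effect of plasma.

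**Working it through.** **1. The plan's own sample size.** Inputs from 6.1 and 6.3: p0 = 0.148, p1 = 0.075, power 80%, overall error 5% (two-sided, which is what 2.289 corresponds to with three Pocock looks).

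Fixed n = (1.960 + 0.842)² × 0.148 × 0.852 / (0.148 − 0.075)² = 185.7. Times the three-look Pocock factor 1.166 this is 216.6, rounded up to 3 × 73 = 219. The stated maximum reproduces. The expected size computes to 153 against the stated 152. The sample size arithmetic is not at fault.

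**2. The decision rule in counts.** With z = 2.289, the upper score limit at observed rate p in n patients is

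U = [p + z²/(2n) + z·√(p(1−p)/n + z²/(4n²))] / (1 + z²/n).

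U is below 14.8% at no more than 3/73, 11/146 or 20/219 events (U = 13.2%, 14.1%, 14.6%). One more event gives 15.1%, 15.0% and 15.1%.

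**3. Baseline.** If the true rate is 14.8%, the exact binomial chance of crossing at some look is 0.35% + 0.50% + 0.59% = 1.4%.

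**4. Effect of mix when plasma does nothing.** Assumptions, not in the documents: the source rate is 14.8% overall; s is its asymptomatic share; r is the untreated risk in asymptomatic workers; a is the enrolled asymptomatic share. Then

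- symptomatic risk: p_s = (0.148 − s·r)/(1 − s)
- untreated rate in the trial: m = (1 − a)·p_s + a·r

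Example: r = 2%, s = 10%, a = 30%. p_s = (0.148 − 0.002)/0.9 = 16.2%; m = 0.7 × 16.2% + 0.3 × 2% = 12.0%. Chance of crossing: 14%.

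Chance of declaring efficacy with inert plasma, r = 2% (untreated rate m in brackets):

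| Enrolled asymptomatic | s = 0% | s = 10% | s = 20% | s = 30% |
|---|---|---|---|---|
| 20% | 11% (12.2%) | 5% (13.4%) | 1.4% (14.8%) | 0.3% (16.6%) |
| 30% | 26% (11.0%) | 14% (12.0%) | 6% (13.2%) | 1.4% (14.8%) |
| 50% | 72% (8.4%) | 59% (9.1%) | 42% (10.0%) | 23% (11.1%) |

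Where the two shares are equal, the chance is the 1.4% baseline. Where fewer are enrolled than in the source (20% against 30%), the untreated rate exceeds 14.8% and the bias is against plasma.

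Other values of r with s = 0%: at r = 5%, 15% (a = 30%) and 44% (a = 50%); at r = 10%, 5% and 10%; at r = 14.8%, no effect.

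**5. Precision of an analysis restricted to entrants with symptoms or pneumonia.** U at an observed 7.4% (half of 14.8%):

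| Set | n | Upper limit |
|---|---|---|
| All Group 4, final look | 219 | 12.5% |
| 30% asymptomatic, looks 1, 2, 3 | 51, 102, 153 | 20.3%, 15.6%, 13.8% |
| 50% asymptomatic, final look | 110 | 15.2% |

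At a true 7.4%, the chance of clearing 14.8% at some look is 88% for the pooled group and about 68% for the symptomatic set with 30% asymptomatic.

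**The case against.** The strongest reply is that the size of the effect depends on a source that cannot be inspected here. Section 1.2 speaks of infected workers, not symptomatic ones, so the 14.8% may already include people without symptoms. Taking the source share as zero is the worst case on that axis. If the source had the same mix and risks, the bias vanishes; if it had more asymptomatic workers than the trial enrols, plasma is disadvantaged. This stands, and it is why the result is given as a range.

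A reader might infer that the entry mix decides the Group 4 result, or that the bias must favour plasma. The documents support neither: they give no asymptomatic risk and no share for the source or the trial, and at a 10% risk the effect is modest. A reader might also infer that the trial report would hide the mix. That is not shown either: entry status has to be known for eligibility (3.1.2.2, 4.1.2), and days of symptoms are recorded for all groups (5.1.1). The plan is silent on tabulating outcomes by these data; silence does not establish that they would be left out.

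Two further replies bear on the remedy. A supportive analysis leaves the pooled rule in charge, so the crossing probabilities above stay as they are. And 14.8% may not be an exact benchmark even for symptomatic entrants, since section 1.2 does not say that workers already severe when first seen were excluded, whereas Group 4 cannot enrol them. Both are fair limits on what the change achieves. Neither removes the reason for it.

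**Conclusion.** The point holds in conditional form. The plan pools three entry states, tests them against a benchmark of unstated symptom mix, and pre-specifies nothing that would show whether a crossed boundary rests on asymptomatic entrants. A false claim through mix needs two conditions that the documents neither establish nor exclude: a lower untreated risk in asymptomatic workers, and a larger asymptomatic share in the trial than in the source.

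At an assumed 2% asymptomatic risk, and source shares from 0% to 30%, the chance of declaring inert plasma effective runs from 26% down to 1.4% with 30% enrolled asymptomatic, and from 72% down to 23% with 50%. At an assumed 10% risk and a source share of 0% it is 5% and 10%. The reference is 1.4%. This is a worthwhile, inexpensive improvement to the analysis plan; it does not show that the Group 4 test is invalid.

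**What to change.** In section 6.3, for Group 4:

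- Pre-specify, as a supportive analysis beside the pooled result, the count, rate and score interval (critical value 2.289) separately for asymptomatic entrants and for entrants with symptoms or pneumonia.
- Compare the rate in the symptomatic set with 14.8%.
- State the symptom mix of the source of 14.8%, or that it is unknown.
- State that an efficacy conclusion resting on the asymptomatic entrants is not attributed to plasma for Group 4 as a whole, but is worded for the entry categories in which it is seen.

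The pooled rule, the sample size and the chance of crossing stay as planned; what changes is the conclusion that may be drawn. The data are already needed for eligibility.

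The cost is precision. The symptomatic analysis will often be inconclusive, above all at interim looks: with 30% asymptomatic, an observed 7.4% clears 14.8% only at the final look, and with 50% not even then. The pooled rule would also stop by the second look about 62% of the time at a true 7.4% (20% + 41%, before rounding), so the full symptomatic number would often not be reached. The plan should therefore say that an inconclusive symptomatic interval is not evidence against plasma.

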6.2 Secondary Endpoints

6.2.1

Secondary endpoints will be analyzed for potential efficacy and statistically compared to historical or matched controlled comparison population. For patients with severe disease, the expected rate of ICU admission is 19.%, with 38.7% requiring mechanical ventilation (14.5% invasive), 94.6% had radiographic abnormalities of the chest, 15.6% developing acute respiratory distress syndrome, and median hospital stay of 13 days. A total of 14% of patients with COVID-19 disease developed severe disease.

6.2.2

Impact of donor sera neutralizing antibody titer will be correlated to clinical outcome.

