1.2 Clinical Characteristics of COVID-19 Disease

In the largest published review from Wuhan China, 1099 patients were followed with confirmed COVID-19 infection. A primary composite end-point event occurred in 67 patients (6.1%), including 5% who were admitted to the ICU, 2.3% who underwent invasive mechanical ventilation, and 1.4% who died. The majority of patients (58%) received intravenous antibiotic therapy and oxygen was administered in 41.3% of patients. CT radiograph was performed on 975 patients and it showed ground-glass opacities in 56.4%, local patchy shadowing in 41.9% and bilateral patchy shadowing in 51.8% and interstitial abnormalities in 14.7%. Chest radiographs were performed in 274 patients and abnormalities were documented in 59.1% (20.1%, 28.1%, 36.5% and 4.4%; respectively). In severe cases, radiographic abnormalities were seen on CT study in 94.6% of patients. For hospitalized patients, fever was present in 88.1% of non-severe and 91.9% of severe patients.

A total of 173 patients were classified as having severe disease per the guidelines of the American Thoracic Society guidelines. For those 926 that presented with non-severe disease, 35.7% required oxygen, 2.4% required ICU admission and none required mechanical ventilation. For those with severe disease, 71.1% required oxygen therapy, 19.1% were admitted to the ICU and 38.7% required mechanical ventilation. The median length of hospital stay for the non-severe was 11 days (10-13) and for the severe 13 days (11.5-17). Death occurred in 0.1% of the patients with non-severe disease and 8.1% of patients with severe disease. For patients presenting with severe disease 71.1% required oxygen therapy, 15.6% developed acute respiratory distress syndrome, admission to the ICU was 19.1%, 38.7 percent required mechanical ventilation (14.5% invasive and 32.4% noninvasive) and median hospital duration was 13 days.

Correlate laboratory studies included C-reactive protein that was elevated above 10 mg/L in 81.5% of those with severe disease and in 56.4% with non-severe disease. Procalcitonin

greater than 0.5 ng/mL was seen in only 3.7% of those with non-severe disease and 13.7% with severe disease presentation.

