3.1.1 Primary and Secondary Endpoints and Efficacy Assessments

The primary endpoint of the study will be:

- 1) progression to severe disease for those with high-risk disease that present with mild/non-severe disease, and
- 2) progression to severe disease for health care workers who present with asymptomatic, mild or non-severe disease.

Secondary endpoints will include:

- 1) Acute care facility/hospital length of stay
- 2) Number of days requiring oxygen support
- 3) Number of days in an intensive care unit
- 4) Number of days on mechanical ventilation (invasive, noninvasive and ECMO)
- 5) Incidence of viral disease associated cardiomyopathy
- 6) Incidence of multi-organ dysfunction/failure
- 7) Safety of transfusion—Incidence of severe adverse events

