4.1.1 Group 3: High Risk Patients with Mild or Non-severe Disease

- 1. Mild Disease: upper respiratory symptoms, cough, gastrointestinal symptoms (emesis, diarrhea, abdominal pain) or fever; but no radiograph evidence for viral pneumonitis.
- 2. Non-severe Disease: Chest radiographic changes compatible with COVID-19 disease, but no signs of respiratory compromise or hypoxemia.
- 3. High Risk condition must include one of the following: Immunocompromised (e.g. neutropenia, active chemotherapy for cancer or hematological malignancy, less than 12 months after undergoing allogeneic hematopoietic stem cell transplant or 100 days from autologous hematopoietic stem cell transplant, on systemic immunosuppressive therapy, history of solid organ transplant and poorly controlled HIV disease (e.g. CD4, 250/uL, recurrent opportunistic infections), insulin dependent diabetes mellitus, moderate to severe asthma history, severe COPD (DLCO < 60), morbid obesity (BMI ≥ 40),age ≥ 65 years, hypertension, moderate or severe cardiac disease (eg. Cardiomyopathy, CHF, moderate or

- severe valvular stenosis, ischemic heart disease), patients with severe renal disease (e.g. on dialysis), or liver disease
- 4. Informed consent signed within 14 days of symptoms developing for mild disease. For patients in the non-severe cohort, the time to consent must be within 14 days of positive chest x-ray or 14 days of first symptom whichever is longer (maximum 14 days to enrollment).

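### The secondary-endpoint benchmarks in Section 6.2.1 come from patients who presented with severe disease, whom neither group enrolls, and for ICU and ventilation they are proportions while the endpoints are day counts

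*Combined protocol and SAP*

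**What the plan says.** Section 6.2.1 commits to a test: "Secondary endpoints will be analyzed for potential efficacy and statistically compared to historical or matched controlled comparison population". It then gives its figures: "For patients with severe disease, the expected rate of ICU admission is 19.%, with 38.7% requiring mechanical ventilation (14.5% invasive", followed by radiographic, ARDS and hospital-stay figures for the same kind of patient. It closes with a general severity rate: "A total of 14% of patients with COVID-19 disease developed severe disease".

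Section 1.2 shows the source, a review of 1,099 patients of whom 173 were classified as severe: "For those with severe disease, 71.1% required oxygen therapy, 19.1% were admitted to the ICU and 38.7% required mechanical ventilation". The same section reports the other patients in that review: "For those 926 that presented with non-severe disease, 35.7% required oxygen, 2.4% required ICU admission and none required mechanical ventilation". Section 6.2.1 does not carry those figures over.

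Section 4.1.1 defines Group 3 as "High Risk Patients with Mild or Non-severe Disease". Section 4.1.2 defines Group 4 as health care providers whose disease is asymptomatic, mild or non-severe.

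Section 3.1.1 lists the ICU and ventilation endpoints as "Number of days in an intensive care unit" and "Number of days on mechanical ventilation (invasive, noninvasive and ECMO". Section 6.3 specifies an intention-to-treat analysis of everyone enrolled. For the comparison with published experience it names a score test for two proportions, with a p value and a 95% interval.

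**The concern.** The trial has no concurrent control, so a test on a secondary endpoint can be no better than its external comparator. The comparator figures printed in Section 6.2.1 describe people who were already severely ill at presentation. Nobody may enter either group in that state.

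The section does not say which trial patients the figures are to be set against, or how a matched population would be built. Neither obvious use is sound:

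- **Against all enrolled patients**, the trial group starts less ill than the benchmark group, so the comparison favors plasma whatever plasma does.
- **Against progressors only**, the severity gap largely closes. But progression is the primary endpoint and happens after transfusion, so the compared subset is itself shaped by treatment, and it is not the all-enrolled analysis of Section 6.3.

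The scales also differ. A proportion admitted to ICU is not a benchmark for days in ICU, and a two-proportion test does not analyze day counts. At stake is whether a claim of secondary benefit on ICU use or ventilation could be trusted.

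**Working it through.** **1. Confirm where the benchmark comes from.** Inputs from Section 1.2: 926 non-severe presenters with 2.4% ICU use; 173 severe presenters with 19.1% ICU use and 14.5% invasive ventilation; whole-review rates of 5% and 2.3%.

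- ICU overall = (926 × 0.024 + 173 × 0.191) / 1,099 = (22.2 + 33.0) / 1,099 = 5.03%, against the stated 5%.
- Invasive ventilation overall, with none among non-severe presenters = 173 × 0.145 / 1,099 = 25.1 / 1,099 = 2.3%, as stated.

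So the Section 6.2.1 figures are the severe-subgroup rates. The ICU figure is 19.1 / 2.4, about 8 times the non-severe rate, and 19.1 / 5, about 4 times the whole-review rate.

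**2. Set endpoints beside benchmarks and test.**

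| Section 3.1.1 endpoint | Figure in 6.2.1 | Test in 6.3 |
|---|---|---|
| Days in ICU | Proportion admitted | Two proportions |
| Days ventilated | Proportion ventilated | Two proportions |
| Length of stay | Median of 13 days (severe) | None for durations |
| Cardiomyopathy, multi-organ failure, severe adverse events (incidence) | None | Two proportions |

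The endpoints that suit the named test have no benchmark. The ICU and ventilation endpoints have a benchmark on another scale. For stay, Section 1.2 gives 11 days for non-severe presenters, but Section 6.2.1 prints only the 13.

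**3. Illustrate the all-enrolled use.** This is conditional: the plan does not state it, and it needs a binary ICU-admission endpoint that Section 3.1.1 does not list.

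- History: 173 × 0.191 = 33, so 33/173, held fixed.
- Trial size: n = 228, the Group 3 maximum in the Section 6.1 table. Section 6.3 describes no futility stop. If untreated progression equals the 25% null, the Pocock boundary allows a false efficacy finding in about 5% / 2 = 2.5% of trials over all three looks, so an inert product nearly always reaches the maximum.
- Test: pooled score statistic z = (x/n − 33/173) / √[p(1 − p)(1/n + 1/173)], with p = (x + 33)/(n + 173). Benefit is declared if z ≤ −1.96.

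At x = 27: p = 60/401 = 0.1496, standard error 0.0360, difference 0.1184 − 0.1908 = −0.0723, z = −2.01. At x = 28, z = −1.88. A benefit is therefore declared at 27 or fewer ICU admissions (11.8%). The probability is the binomial P(X ≤ 27):

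| Assumed untreated ICU rate | History fixed | History redrawn as Binomial(173, 33/173) |
|---|---|---|
| 10% | 85% | 74% |
| 12% | 52% | 51% |
| 15% | 10% | 19% |

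Group 4 at its maximum of 219 gives 85%, 53% and 11% with history fixed.

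The documents give no untreated ICU rate for these groups. If ICU use came only from progressors at the Section 1.2 severe rate, Group 3 would have 0.25 × 0.191 = 4.8%. The rates in the table are set higher on purpose, because high-risk patients may need ICU more often than that review suggests.

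**4. Illustrate the progressor-only use.** Let the number of progressors be Binomial(228, 0.25), with mean 57, and let their true ICU rate be 19.1%. The same test then declares a benefit in about 1% of trials (about 2% with history redrawn). At exactly 57 progressors it requires 4 or fewer admissions, with probability 0.97%. The false benefit in step 3 therefore comes from the denominator.

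**The case against.** The strongest reply is that the sentence carries its own denominator. It opens by limiting itself to severe disease, and in a trial of milder patients that most naturally means those who become severe, or plain background. On that reading step 4 applies and the false-benefit rate is about 1%. This is a fair reading, and the plan does not contradict it. It does not make the comparison sound, because the comparison would still condition on an event after treatment and would not be the analysis set in Section 6.3.

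Second, the comparator is left open. A matched population is allowed, and nothing makes the printed rates null values. That stands. But no source, matching variables or method are given, and the printed figures are the only ones offered.

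Third, the probabilities in step 3 combine a denominator and a binary endpoint that the plan does not state, and they range from 10% to 85% with an untreated rate that the documents do not supply. That also stands, which is why they are an illustration only.

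Fourth, the sentence may be left over from groups since dropped. The Overview of Study Design still sizes Groups 1 and 2, and Section 3.1 still speaks of four treatment groups. This is an inference, since the current text does not define those groups. If it is right, the fix is simpler still.

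**Conclusion.** The point holds in a limited form. The ICU, ventilation, ARDS and stay figures that Section 6.2.1 calls expected describe a population that neither group enrolls. They are not a valid comparator for all enrolled patients, and for ICU and ventilation they are on a different scale from the listed endpoints. Restricting them to progressors removes the severity bias, provided progressors resemble severe presenters, but brings in conditioning on a post-treatment event.

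A reader might infer that the plan sets 19.1% as the null for everyone enrolled, or that a false secondary benefit is close to certain. The documents support neither. No such use is written down, and the size depends on the untreated ICU rate: at n = 228, about 85% at 10%, 52% at 12% and 10% at 15%, assuming a pooled score test at two-sided 5%, history fixed at 33/173 and an inert product. No false-benefit rate is claimed here for ARDS, radiographic findings or length of stay.

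A reader might also infer that the main result is compromised. It is not: the primary test of progression, the Pocock boundary and the sample size do not use these figures. This should be fixed before secondary results are analyzed, but it does not threaten the trial's main conclusion.

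**What to change.** Rewrite Section 6.2.1 as follows:

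1. Remove the severe-presenter figures, or label them as descriptive background that is not used in any test.
2. Require any historical or matched control used for a test to have the same severity at entry and the same risk category as the group: high-risk patients with mild or non-severe disease for Group 3; health care providers with asymptomatic, mild or non-severe disease for Group 4.
3. Limit the Section 6.3 score test to incidence endpoints.
4. Report day-count endpoints descriptively unless comparable control data on days exist.

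The non-severe figures in Section 1.2 (2.4% ICU, no ventilation) should not be swapped in as fixed nulls. They are not specific to high-risk patients. They also sit poorly with the 25% progression assumed in Section 6.1, since progressors alone at the 19.1% severe rate would give 4.8% ICU use.

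The cost is one paragraph of text. The downside is that, if no comparable control is found, the secondary outcomes are descriptive only and a secondary benefit is harder to claim.
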